# 6.2.4 Analysis of AE data

Analysis of AE data will primarily be descriptive based on DAIDS toxicity table coding of events. Rates of AE will be compared between randomized arms using Fisher's Exact Test.

# 6.2.5 Analysis of the anti-SARS-CoV-2 levels and inflammatory markers.

Analysis of antibody levels will primarily be descriptive, comparing the geometric mean antibody levels at days 1,2,5,8,15, 29, and 120 between the randomized arms. Furthermore, it is of interest to describe the entire distributions of anti-SARS-CoV-2 antibody levels by randomized arms and contrast these distributions. Therefore, we will use quantile regression in order to describe whether there is a shift or change in the titer distribution between randomized arms. Given that repeated measures of antibody levels will be obtained, we will account for the correlation in measures within individuals using a cluster bootstrap

33

in order to properly estimate the p-value and 95% confidence intervals. Similar analysis will also be applied to lymphocyte counts on days 1,2,5,8,15, 29 hematological measurements (D-dimer, ferritin, hsCRP) on days 1,2,5,8,15, 29, 29, and other lab measures showing right-skewed distributions. Exploratory analyses of antibody isotypes, neutralizing antibody activity, antibody affinity, glycosylation and T-cell responses will be conducted to compare between arms and over time.

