#### **Clinical, Laboratory and Imaging Data**

- 1. Date of symptom onset and history of presenting illness
- 2. Demographics: Age, sex, comorbidities, zip code + 4
- 3. Vital Signs: Temperature, respiratory rate, blood pressure, oxygen saturation, oxygen requirements, APACHE score, SOFA score.
- 4. Laboratory Data:
  - Hematologic Markers: CBC with differential (neutrophil, lymphocyte counts explicitly recorded), PT/PTT, D-dimer
  - Metabolic Markers: Creatinine, liver function tests
  - Inflammatory Markers: CRP, ferritin
  - Arterial blood gas values, if available
  - Measurement of isotype, total antibody, and neutralizing capacity of donor plasma antibodies to SARS-CoV-2
  - Serum or plasma antibody to SARS-CoV-2: Day 1, 5,8,15, 29, 120
  - SARS-CoV-2 PCR from nasopharyngeal swab (NP) or mid-turbinate nasal swab (MTN Day 1,2,5,8,15
- 5. Chest imaging (CT or Chest x-ray): obtained as part of standard care

**Primary Objective:** Evaluate the efficacy of convalescent fresh frozen plasma from blood donors who have recovered from Covid-19 containing antibodies to SARS-CoV-2 versus control (standard fresh frozen plasma) to prevent severe hypoxemia during the 14 days after administration in hospitalized patients with COVID-19 who are within 72 hours of hospital admission OR 14 days of symptom onset.

**Primary Endpoint**: Progression to mechanical ventilation/ECMO for hypoxia/hypercarbia, or death from any cause

Safety and Efficacy of the intervention will be assessed during multiple time points Day 1 (baseline), 2,5,8,15, 29 and once at month 4 (day 120).

OBJECTIVES	ENDPOINTS (OUTCOME MEASURES)
Primary Objective	
Evaluate the efficacy of convalescent fresh frozen plasma from blood donors who have recovered from Covid-19 containing antibodies to SARS-CoV-2 versus control (standard fresh frozen plasma) to prevent mechanical intubation or death within 14 days of CPP administration in hospitalized patients with COVID-19 who are within 3 days of hospital admission or 14 days of symptom onset.	Progression to mechanical ventilation or death within the first 14 days of enrollment. A secondary endpoint will evaluate progression to endpoint within the first 28 days of enrollment.
Key Secondary Objectives	

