# 5.4 Study procedures

#### Table 1: Schedule of Evaluations

Study period	Screen	Enrollment	Transfusion (within 24 hours of randomization)	Follow up					
Day	Within 3d prior to enrollment	1 (values within 24 hours prior to enrollment)	1	2	5	8	15	29	120
Visit window					+/-	1 day		+/- 7d	+/- 14d
Eligibility									
Informed consent	Х								
Demographic and Medical history	x								
COVID-19 symptom screen	x								
SARS-CoV-2 RT- PCR for eligibility	within 14								
Pregnancy test	days -								
ABO for plasma compatibility	x								
Chest imaging (CXR or CT scan)	х								
Oxygenation Status	х	Х							
		Study I	Drug Administration						
Randomization		Х							
Drug infusion			Х						
Study Procedures									
Vital signs		Х	XXX 		ily days		x 		
Oxygenation status		Х		d	aily 2-8	3 	х	х	Х

Symptom screen	Х	Х	x	x	х	х	х	х	x
Day	Within 3d prior to enrollment	Enrollment (values within 24 hours prior to enrollment)	Plasma transfusion	2	5	8	15	29	120
Visit window				+/-1 day				+/- 5d	+/- 14d
Concomitant medications		x		x	x	x	(only	x COVID t related	reatment 1)
Assessment with 8- point ordinal scale		x		x	х	х	х	x	x
Assessment with WHO 11 point ordinal scale							x	x	
Chest imaging (CXR or CT scan) 					х		х		
Laboratory testing									
CBC (with absolute lymphocyte count)		х		x 	Х 	Х 	X 	X 	х
Renal function, liver function test		х		x 	Х 	Х 	X 		
PT, PTT, D-dimer, hsCRP, ferritin		х		x 	x 	X 	x 	x 	x
SARS-CoV-2 RT- PCR(NP/MTN swab) 		х		x	X 	X 	x 		
Blood for future testing (includes SARS-CoV-2 Ab) 		Х			x 	x 	x 	X 	X 

Vital sign testing, immediately prior to infusion, 10-20 minutes after start of infusion, at completion of infusion and 30-60 minutes after the end of the infusion, ideally bundled with other required clinical care.  If still hospitalized.

 Record most recent preceding chest imaging, if available and conducted per standard of care

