  Record lab values if collected as part of standard of care. Will encourage clinical teams to collect but will not be required.
  Blood drawn if in-person visit is feasible

Prioritize day 1 research blood collection and nasal swab. Collect on day 5, 8, 15 if feasible

CAPRI AUAPLIVE PIOLOCOL VEL 5.0 7/20/2020

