# Day 2-15 (if remain hospitalized)

1. Vitals signs (day 2-8)

- 3. Assessment of clinical status (8-point ordinal scale) (days 2,5,8)
- 4. New medical conditions, concomitant medications, AE evaluation (days 2,5,8)

6. Oxygenation status: current FiO2 or liters of O2, route of oxygen, and oxygen saturation or PaO2 (if available) (days 1-8)

7. Nasopharyngeal or mid-turbinate nasal swabs, if feasible (days 2,5,8)

8. Stored samples for future studies(3 EDT tubes and 1 SST) (day 5, 8 only) if feasible. This testing includes SARS-CoV-2 antibody testing

10. CXR (or CT with increased oxygen requirement): day 5,(record most recent imaging prior to day 5, conducted per standard of care)

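### Section 6.2.5 compares antibody levels on Day 2, when no antibody sample is scheduled, and lists the pre-infusion Day 1 sample as a comparison day without adjusting for it

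*Combined protocol and SAP*

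**What the plan says.** Section 6.2.5 describes the antibody analysis as mainly descriptive, "comparing the geometric mean antibody levels at days 1,2,5,8,15, 29, and 120 between the randomized arms". It adds quantile regression to compare the antibody distributions between arms. A cluster bootstrap handles repeated measures and supplies p-values and 95% confidence intervals. No baseline covariate or change from Day 1 is mentioned.

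The sampling plan appears in four places:

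- Section 3, laboratory data list: "Serum or plasma antibody to SARS-CoV-2: Day 1, 5,8,15, 29, 120".
- Section 5.4, Table 1, row "Blood for future testing (includes SARS-CoV-2 Ab": marked at enrollment and on Days 5, 8, 15, 29 and 120. The Day 2 cell is blank.
- Table 1, footnote 7: "Prioritize day 1 research blood collection and nasal swab. Collect on day 5, 8, 15 if feasible".
- Section 5.4, visit text for Days 2-15, on stored samples: "day 5, 8 only) if feasible. This testing includes SARS-CoV-2 antibody testing".

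On the status of Day 1, section 3 gives the assessment times as "Day 1 (baseline), 2,5,8,15, 29 and once at month 4 (day 120". Table 1 puts the first research blood in the enrollment column, headed "values within 24 hours prior to enrollment", which is separate from the transfusion column.

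**The concern.** There are two separate problems. First, the analysis section names a day on which the protocol collects no antibody specimen. A statistician following section 6.2.5 would have nothing to analyse on Day 2. The first recipient sample after the infusion is Day 5, and only if the patient is still in hospital and collection is feasible. By then a single passive dose is being read against several further days of the patient's own response.

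Second, a between-arm contrast on a pre-infusion sample cannot show a treatment effect; it shows only chance imbalance. The value of Day 1 is as a covariate. Entry is allowed within 72 hours of admission or within 14 days of first illness, so patients' own starting levels may differ widely. With 25 per arm, some imbalance is likely.

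At stake is how well the trial can describe the antibody increment in recipients. Section 4.1.2 also says that the trial will compare immune responses between arms to look for attenuation after convalescent plasma. Section 6.2.5 is where antibody responses are compared.

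**Working it through.** **Step 1. Match analysis days to sampling days.**

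- Analysis days (6.2.5): {1, 2, 5, 8, 15, 29, 120}, seven days.
- Sampling days (section 3 list and Table 1 row): {1, 5, 8, 15, 29, 120}, six days.
- Analysis minus sampling = {2}. Sampling minus analysis = empty.

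Day 2 is the only mismatch. It is not a reading error in a broken table, because the section 3 list, footnote 7 and the visit text are ordinary text and agree with the blank cell. Removing Day 2 leaves Day 1 plus five post-infusion days (5, 8, 15, 29, 120).

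**Step 2. Check what is drawn on Day 2.** Table 1 does mark clinical laboratory tests that day if the patient is still hospitalized: the row "CBC (with absolute lymphocyte count", chemistry, and PT, PTT, D-dimer, hsCRP and ferritin. CBC and chemistry are recorded only if done as standard care. Blood may therefore be drawn on Day 2; what is missing is a scheduled antibody specimen.

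**Step 3. Size of the baseline point.** The plan states no figure here to reproduce. The documents give n = 25 per arm (section 6.1) but no antibody SD and no correlation. Both are assumed below, for illustration only.

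- SE of the arm difference in mean log10 level = SD × √(2/25) = 0.283 × SD.
- SD 0.5: SE = 0.141, and 10^0.141 = 1.4-fold in the geometric mean ratio. SD 1.0: SE = 0.283, and 10^0.283 = 1.9-fold.
- With linear adjustment for log Day 1 level at correlation r, the SE is multiplied by √(1 − r²).
- Difference detectable with 80% power, two-sided 0.05, in SD units = (1.96 + 0.84) × 0.283 × √(1 − r²).

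| r (assumed) | √(1 − r²) | SE cut | SE, SD 0.5 | SE, SD 1.0 | Detectable (SD) |
|---|---|---|---|---|---|
| 0 (unadjusted) | 1.000 | 0% | 0.141 | 0.283 | 0.79 |
| 0.3 | 0.954 | 5% | 0.135 | 0.270 | 0.76 |
| 0.5 | 0.866 | 13% | 0.122 | 0.245 | 0.69 |
| 0.7 | 0.714 | 29% | 0.101 | 0.202 | 0.57 |
| 0.8 | 0.600 | 40% | 0.085 | 0.170 | 0.48 |

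These figures suppose that all 25 per arm are sampled. Days 5, 8 and 15 depend on the patient still being in hospital and on feasibility, so the real standard errors would be larger. The formula applies to linear adjustment of log means. It does not give the gain for quantile regression.

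**The case against.** The strongest reply is that this is a drafting slip in a secondary, mainly descriptive analysis. The same section lists Day 2 for lymphocytes, D-dimer, ferritin and hsCRP, which Table 1 does mark on Day 2, so the numeral may simply have been carried across. No listed objective is an antibody endpoint. Arms are randomized 1:1, so patients' own responses balance in expectation and the unadjusted contrast is valid. Showing Day 1 beside later days at least reveals any imbalance. Day 5 is also informative, since section 4.1 says that transferred antibody can protect for weeks to months.

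Most of that stands. It limits the consequence but leaves the mismatch in place. Section 6.2.5 also promises p-values and confidence intervals, so its specification matters. The cluster bootstrap corrects standard errors for within-person correlation; it does not adjust for baseline.

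A reader might infer three stronger things that the documents do not support:

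- That no blood is drawn on Day 2. Table 1 marks clinical tests that day.
- That the antibody dose delivered goes unmeasured. Section 3 lists isotype, total antibody and neutralizing capacity of donor plasma, section 4.1.6 has every convalescent unit tested, and section 5.3.4 stores a sample for quantitation. The gap is in early recipient levels, which is a different quantity.
- That omitting the baseline biases the comparison. Under randomization it costs precision and leaves chance imbalance uncorrected.

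**Conclusion.** The point holds in two parts. The Day 2 mismatch is certain: one of seven stated antibody comparisons has no scheduled data, and the recipient's early rise is not captured before about Day 5. The missing baseline adjustment is a loss of precision. Under the assumed correlations of 0.5 to 0.8 the avoidable part of the standard error is about 13% to 40%; at 0.3 it would be only about 5%. Those sizes rest on assumed correlations, full sampling of 25 per arm, and linear adjustment of log levels. The effect is confined to the antibody analysis in section 6.2.5. The primary endpoint and its Fisher exact test are untouched.

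**What to change.** 1. Delete Day 2 from the antibody days in section 6.2.5. It can stay for the laboratory markers that Table 1 does schedule. This costs wording only.
2. If the sponsor prefers to keep Day 2, add a research tube to a Day 2 draw, mark it in Table 1, and align the section 3 list, footnote 7 and the visit text. The sample must be timed after the infusion ends, with the time recorded. Section 5.3.6 allows infusion up to 24 hours after randomization, so the routine Day 2 draw may fall too early for some patients and a separate draw may be needed. The volume is small against the 500 mL limit in section 7.1.1.
3. Define Day 1 in section 6.2.5 as the pre-infusion baseline. State in the Day 1 visit text that the research blood is taken before the infusion starts, because that list gives no order.
4. For each later day, report the arm difference in log antibody level, as a ratio of geometric means with 95% confidence interval, adjusted for log Day 1 level. Include Day 1 as a covariate in the quantile regression, and show the unadjusted distributions alongside. Show Day 1 by arm as a description, without a test.

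Items 3 and 4 need no new data: the Day 1 sample is already the one that sites are told to put first.

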# 6.2.6 Analysis the rates, levels and duration of SARS-CoV-2 RNA in NP/MTN swabs

This secondary analysis will be primarily descriptive. The proportion positive at days 1,2,5,8, and 15 and whether individuals lose positivity status at a subsequent visit among those who were initially positive will be examined. To determine the proportion that are positive at each visit, we will do a pooled complementary log-log model in order to describe the cumulative incidence of SARS-CoV-2 positivity over time. The pooled complementary log-log model is a discrete time-to-event-analysis that estimates the log hazard rate at each discrete time point. Similar to the analysis of anti-SARS-CoV-2 antibody levels, the goal of this secondary aim is to describe the distribution of SARS-CoV-2 RNA between randomized arms. Therefore, we will use the same approach as that for the anti-SARS-CoV-2 antibody levels. Because the exact day that an individual becomes negative is not known, a minimum and maximum amount of positive time will be used to describe the positive duration of each individual. If the sample is adequate, we will describe the duration of positivity using a non-parametric approach for time-to-event analysis.

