To evaluate the clinical efficacy of CCP relative to the control arm in adults hospitalized with COVID-19 according to clinical status (8-point ordinal scale) at Day 29	
 
Death;
 
Hospitalized, on invasive mechanical ventilation or ECMO;
 
Hospitalized, on non-invasive ventilation or high flow oxygen devices;
 
Hospitalized, requiring supplemental oxygen;
 
Hospitalized, not requiring supplemental oxygen - requiring ongoing medical care (COVID-19 related or otherwise);
 
Hospitalized, not requiring supplemental oxygen - no longer requires ongoing medical care;
 
Not hospitalized, limitation on activities and/or requiring home oxygen;
 
Not hospitalized, no limitations on activities.
 

OBJECTIVES	ENDPOINTS (OUTCOME MEASURES)
Additional Secondary Objectives	

 
To evaluate the clinical efficacy of different investigational therapeutics as compared to the control arm as assessed by:
 
Clinical Severity Ordinal scale:
 
Time to an improvement of one category and two categories from Day 0 (baseline) using an ordinal scale.
 
Subject clinical status using ordinal scale at Days 2,5,8,15, 29
 
Mean change in the ordinal scale from Day 1 to Days 2,5,8,15, 29
 
	
 
Clinical outcome assessed using ordinal scale daily while hospitalized and on Days 15, 29 and 120
 
Time to clinical recovery (defined as ordinal score 1-3)
 

 
National Early Warning Score (NEWS):
 
Time to discharge or to a NEWS of ≤ 2 and maintained for 24 hours, whichever occurs first.
 
Change from Day 1 to Days 2,5,8,15, 29
 
	
 
NEWS assessed daily while hospitalized
 

 
Oxygenation:
 
Oxygenation use up to Day 120.
 
Incidence and duration of new oxygen use during the study.
 
Oxygen requirement on day 1,2,5,8,15, 29
 
	
 
Days of supplemental oxygen (if applicable) up to Day 29
 
PaO2/FiO2 ratio or SpO2/FiO2
 
O2 requirement at day 120
 

 
Non-invasive ventilation/high flow oxygen:
 
Non-invasive ventilation/high flow oxygen use up to Day 29.
 
Incidence and duration of new non-invasive ventilation or high flow oxygen use during the study.
 
	
 
Days of non-invasive ventilation/high flow oxygen (if applicable) up to Day 29
 

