
 
Invasive Mechanical Ventilation / extracorporeal membrane oxygenation (ECMO):
 
Ventilator / ECMO use up to Day 29.
 
Incidence and duration of new mechanical ventilation or ECMO use during the study.
 
	
 
Days of invasive mechanical ventilation/ECMO (if applicable) up to Day 29.
 

 
Hospitalization
 
Duration of hospitalization (days).
 
	
 
Days of hospitalization as of Day 29 and day 120
 

Mortality 
 
15-day mortality
 
29-day mortality
 
120-day mortality
 
	
 
Date and cause of death (if applicable)
 

To evaluate the safety of CCP as compared to the control arm as assessed by:	• SAEs

 
Cumulative incidence of SAEs through Day 29.
 
Cumulative incidence of Grade 3 and 4 clinical and/or laboratory AEs through Day 29.
 
Transfusion associated adverse events
 
	
 
Grade 3 and 4 AEs
 
Grade 2 or higher AE's attributed to CCP
 

 
Exploratory Objectives
 
To evaluate the virologic efficacy of CCP
 
	

 
as compared to the control arm as assessed by:
 
Percent of subjects with SARS-CoV-2 detectable in nasal sample at Days 1,5,8,15
 
Quantitative SARS-CoV-2 virus in NP/MTN sample at Days 1,2,5,8,15
 
	
 
Qualitative and quantitative polymerase chain reaction (PCR) for SARS-CoV-2 in NP/MTN swab on Day 1,2,5,8,15 (while hospitalized)
 

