# 4.1.7 Viral load testing

Serial nasopharyngeal testing will be conducted to evaluate SARS-CoV-2 viral decline in each arm. Metagenomic next generation sequencing (mNGS) will be conducted on PCR specimens. mNGS enables simultaneous profiling of host gene expression and viral load, and assessment of the SARS-CoV-2 viral genome. This approach will enable broad detection of host transcriptional biomarkers that may correlate with treatment outcomes, and may reveal biological mechanisms underpinning CCP antiviral activity. mNGS will additionally provide an opportunity to assess whether SARS-CoV-2 viral load and genotype correlate with clinical outcomes and treatment response.

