
 
Oxygenation:
 
Oxygenation use up to Day 90.
 
Incidence and duration of new oxygen use during the study.
 
Oxygen requirement on day 1,2,5,8,15, 29
 
	
 
Days of supplemental oxygen (if applicable) up to Day 29
 
PaO2/FiO2 ratio or SpO2/FiO2
 
O2 requirement at day 120
 

 
Non-invasive ventilation/high flow oxygen:
 
Non-invasive ventilation/high flow oxygen use up to Day 29.
 
Incidence and duration of new non-invasive ventilation or high flow oxygen use during the study.
 
	
 
Days of non-invasive ventilation/high flow oxygen (if applicable) up to Day 29
 

 
Invasive Mechanical Ventilation / extracorporeal membrane oxygenation (ECMO):         
 
Ventilator / ECMO use up to Day 29.
 
Incidence and duration of new mechanical ventilation or ECMO use during the study.
 
 
 
	
 
Days of invasive mechanical ventilation/ECMO (if applicable) up to Day 29.
 

 
Hospitalization
 
Duration of hospitalization (days).
 
	
 
Days of hospitalization as of Day 29 and day 120
 

Mortality 
 
15-day mortality
 
29-day mortality
 
120-day mortality
 
	
 
Date and cause of death (if applicable)
 

To evaluate the safety of CCP as compared to the control arm as assessed by:	• SAEs

 
Cumulative incidence of SAEs through Day 29.
 
Cumulative incidence of Grade 3 and 4 clinical and/or laboratory AEs through Day 29.
 
Transfusion associated adverse events
 
	
 
Grade 3 and 4 AEs
 
Grade 2 or higher AE's attributed to CCP
 

 
Exploratory Objectives         
 
To evaluate the virologic efficacy of CCP as compared to the control arm as assessed by:
 
 
 
Percent of subjects with SARS-CoV-2 detectable in NP/MTN sample at Days 1,5,8,15
 
Quantitative SARS-CoV-2 virus in NP/MTN sample at Days 1,2, 5,8,15
 
	
 
Qualitative and quantitative polymerase chain reaction (PCR) for SARS-CoV-2 in NP/MTN swab on Day 1,2,5,8,15 (while hospitalized)
 

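### The between-arm comparison of SARS-CoV-2 RNA levels does not use each patient's own Day 1 RNA, so it is less precise than the collected data allow

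*Combined protocol and SAP*

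**What the plan says.** The exploratory objectives (Section 3 and Section 5.1) include RNA level as an outcome: "Quantitative SARS-CoV-2 virus in NP/MTN sample at Days 1,2, 5,8,15". Section 4.1.7 gives the purpose: "Serial nasopharyngeal testing will be conducted to evaluate SARS-CoV-2 viral decline in each arm".

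Section 6.2.6 calls the analysis primarily descriptive and sets no model of its own for RNA levels. It says "Therefore, we will use the same approach as that for the anti-SARS-CoV-2 antibody levels". Section 6.2.5 supplies that approach in three parts:

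- a day-by-day comparison of geometric means: "comparing the geometric mean antibody levels at days 1,2,5,8,15, 29, and 120 between the randomized arms";
- a contrast of distributions: "we will use quantile regression in order to describe whether there is a shift or change in the titer distribution between randomized arms";
- a cluster bootstrap for within-patient correlation, from which p-values and 95% confidence intervals are taken.

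Neither section names Day 1 RNA, or any other variable, as a covariate. Neither defines a change from Day 1 for RNA.

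Table 1 schedules a swab at enrollment, and its footnote 7 reads "Prioritize day 1 research blood collection and nasal swab". The Day 5, 8 and 15 swabs are marked for patients still hospitalized and are collected if feasible.

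**The concern.** Day 1 RNA is the outcome itself, measured before treatment. It is likely to be the best single predictor of the later values and the most complete swab in the trial. Section 6.2.5 places it among the compared days, where it contributes nothing to the Day 2 to Day 15 contrasts. The cluster bootstrap gives valid standard errors for repeated measures, but it does not adjust the arm difference for where patients started.

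Entry is allowed within 72 hours of admission or within 14 days of first symptoms, so patients can differ considerably in time since onset. Section 5.3.5 describes 1:1 web-based randomization and mentions no stratification. With about 25 per arm, some chance difference in Day 1 RNA is to be expected, and part of it carries into the later days. At stake are the width of the intervals and how readily an observed RNA difference in this one small trial can be interpreted.

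**Working it through.** The plan gives no power, SD, effect size or correlation for RNA, so there is no figure of its own to reproduce.

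**Inputs from the protocol.** 50 patients randomized 1:1, so 25 per arm (Section 6.1); two-sided 0.05 (Section 6.2.1).

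**Assumptions not in the protocol.** Correlation ρ between Day 1 and later log RNA of 0.3, 0.5 or 0.7; approximately normal log RNA with unit SD; 10 to 25 evaluable patients per arm.

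**Step 1: chance imbalance at Day 1.** The between-arm difference in Day 1 means has SD √(2/n).

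| n per arm | SD of gap | P(gap > 0.25 SD) | P(gap > 0.5 SD) |
|---|---|---|---|
| 25 | √(2/25) = 0.283 | 37.7% | 7.7% |
| 15 | 0.365 | 49.4% | 17.1% |
| 10 | 0.447 | 57.6% | 26.4% |

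An unadjusted later-day contrast carries ρ times the gap. For a 0.5 SD gap this is 0.15, 0.25 or 0.35 SD at ρ = 0.3, 0.5 or 0.7.

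**Step 2: precision gained by adjustment.** The variance factor is 1 − ρ². The equivalent unadjusted sample per arm is 25/(1 − ρ²). The difference detectable with 80% power is (1.960 + 0.842) × √(2/25) × √(1 − ρ²), which is 0.79 SD without adjustment.

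| ρ | 1 − ρ² | Variance saved | Equivalent n per arm | Detectable difference |
|---|---|---|---|---|
| 0.3 | 0.91 | 9% | 27.5 | 0.76 SD |
| 0.5 | 0.75 | 25% | 33.3 | 0.69 SD |
| 0.7 | 0.51 | 49% of variance remains saved as 1 − 0.51 | 49.0 | 0.57 SD |

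**Step 3: does the gain apply to quantile regression?** In 1,500 simulated trials at 25 per arm for each ρ, the adjusted-to-unadjusted variance ratio was 0.95, 0.75 and 0.51 for means and 0.96, 0.72 and 0.51 for median regression. The gain therefore applies to the planned method as well.

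**Step 4: what weakens the gain.** With ρ = 0.5 and half the later values undetectable, a simulation of mean differences put the saving at about 16%, against about 23% with none undetectable. Numbers also fall at later days. Effects of 0.566 and 0.809 SD have 50% and 80% power unadjusted at 25 per arm. At ρ = 0.5, adjustment raises these to 62% and 90%. With 10 per arm the same effects go only from 22% to 28% and from 40% to 50%.

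**The case against.** The strongest reply is that the plan does what it sets out to do. Section 6.2.6 aims to describe the RNA distribution by arm, and the objective lists levels by day. A Day 1 term in quantile regression estimates quantiles conditional on baseline, which is a different target. Section 4.1.7 speaks of decline in each arm, which can be read as a within-arm description. This stands, and it is why the adjusted contrast should be added and should not replace the marginal description. It does not remove the point, because the Section 6.2.5 approach also produces between-arm p-values and confidence intervals.

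Second, this is an omission. The plan gives no model formula and does not rule out covariates. Because Day 1 is reported, an imbalance would be visible. Section 6.2.6 also looks at loss of positivity among those initially positive, which conditions partly on baseline. All of this is true, but displaying an imbalance does not adjust for it, and deciding on adjustment after seeing it leaves a post hoc choice.

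Third, the gain rests on an assumed ρ and on full swab numbers. That also stands: at ρ = 0.3 the gain is small.

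A reader might infer that the planned comparison is biased. The documents do not support that: allocation is randomized, so the unadjusted contrast is right on average and chance imbalance is part of its stated uncertainty.

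A reader might also extend the point to NEWS, whose listed measure is "Change from Day 1 to Days 2,5,8,15, 29". That does not follow. Section 6 specifies no NEWS analysis, and a change-from-Day-1 endpoint does not exclude a Day 1 covariate.

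**Conclusion.** The point holds as a low-cost improvement. The plan collects and prioritises a Day 1 swab and then does not use it to sharpen the between-arm comparison of RNA levels. The loss is in precision and in exposure to chance imbalance; validity is not in question. Its size depends on a correlation that the documents do not give, and it ranges from minor at ρ = 0.3 to substantial at ρ = 0.7, with a reduction where many results are undetectable.

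Two limits remain whatever is done about baseline. Few later swabs will keep absolute power low, and adjustment does not remove missingness caused by discharge. The objective is exploratory, so nothing here bears on the primary comparison of mechanical ventilation or death.

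**What to change.** In Section 6.2.6, keep the descriptive distributions of RNA by arm and day, and add one pre-specified between-arm contrast:

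- outcome: log RNA on Days 2, 5, 8 and 15;
- terms: arm, day, arm-by-day and Day 1 log RNA, with the same quantile regression and cluster bootstrap;
- Day 1 used as baseline only, not as an outcome day in this model;
- a stated value or censoring rule for undetectable results;
- a missing-baseline indicator for patients without a Day 1 swab.

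The cost is SAP wording and some added model terms in a small data set. No new data are needed. The text should say that the adjusted contrast is conditional on Day 1 RNA and supplements the marginal description, and that it does not address swabs missing after discharge.
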